1.0 Objectives

The goal of this pilot study is to determine the precision and accuracy of measurements of intraocular pressure (IOP) when a PROSE (Prosthetic Replacement of the Ocular Surface Ecosystem) scleral lens is on the eye.

The PROSE device (PD) is a specialized scleral lens that is filled with preservative-free saline and then applied to the eye in order to treat a variety of ocular conditions. The PROSE device vaults the cornea without touch and lands gently on the conjunctival tissue overlying the sclera. Because scleral lenses vault and therefore cover the cornea, measuring IOP during lens wear is challenging as traditional techniques rely on corneal contact. Measuring IOP before insertion and after removal of the PROSE device likely does not correspond to the IOP when the lens is actively on the eye.

This is a prospective study of the precision and accuracy of tonometry measurements with scleral lens wear. Three non-traditional means of IOP measurements will be used: scleral TonoPen, scleral pneumatonometry, and transpalpebral Diaton tonometer. Data on precision and accuracy of these instruments in this pilot study aims to guide decision making in a full study on the effects of scleral lenses on IOP.

2.0 Background

The PROSE device is a refractive treatment for individuals with pathologies that require a rigid lens to mask irregularities on the front refracting surface of their eye (the cornea). PROSE is also used in cases of ocular surface disease to protect and support the ocular surface in an effort to reduce dryness, prevent ocular surface breakdown, ulceration, and perforation. The PROSE device is similar to a scleral lens in theory though it allows for unique customizations that are unavailable in currently marketed scleral lens designs, including fenestrations and channels (air and fluid ventilation, respectively).

Recent literature has suggested that intraocular pressure may rise during scleral lens wear, although variability exists in methods and results within the literature.¹⁻³ Possible causes include negative pressure and suction created underneath the lens during settling or due to the pressure applied by the lens on the structures involved in aqueous outflow, namely the trabecular meshwork and the episcleral veins.¹⁻³ The challenge in elucidating this concept is that the scleral lens and its relationship to the cornea is a closed environment that is difficult to study.

Traditional measurements of intraocular pressure rely on corneal contact. Methods of IOP measurement that do not rely on corneal contact instead use either scleral contact (i.e. scleral pneumatonometry and scleral TonoPen) or contact with the eye through the eyelid (transpalpebral Diaton). This study will use these three methods due to the fact that they are the only options currently available to measure IOP without corneal contact, which is a requirement for IOP measurement during scleral lens wear.

An important consideration when using these instruments is that measurements taken over the extraocular muscles may give inaccurate results. Literature suggests that superotemporal and inferotemporal measurements using the pneumatonometer provide the most accurate and

comparable results to a direct corneal measurement perhaps due to the avoidance of measurement over the extraocular muscles.⁴ Scleral pneumatonometry IOP measurements can potentially be used to estimate corneal IOP using a published equation posited by Kuo et al.⁵

3.0 Inclusion and Exclusion Criteria

The participant will be eligible to participate if the following criteria apply:

- 1. Written Informed Consent has been obtained prior to any study-related procedures taking place
- 2. Written documentation has been obtained in accordance with the relevant county and local privacy requirements, where applicable
- 3. Male or female, 18 years of age and older prior to the initial visit
- 4. Has a current diagnosis of corneal ectasia, i.e. keratoconus, pellucid margin degeneration
- 5. Is an established wearer of PROSE in both eyes; without fenestrations or channels; with diameter equal to or greater than 18.0 mm
- 6. Upon examination by the investigator, there is adequate exposure of the sclera as required for IOP measurements with the planned device
- 7. In the opinion of the investigator, the subject has the ability to follow study instructions
- 8. In the opinion of the investigator, the subject has the ability to complete all study procedures and visits

The participant would not be eligible to participate if at least one of the following criteria is met:

- 1. Is aphakic (i.e., missing their natural lens inside the eye)
- 2. Is currently participating in any other type of eye-related clinical or research study
- 3. Is pregnant or nursing as reported by the subject
- 4. Less than 18 years of age
- 5. Has a condition or is in a situation which, in the investigator's opinion, may put the subject at significant risk, may confound study outcomes, or may significantly interfere with the subject's participation in the study
- 6. Has had previous ocular surgery within the past 12 weeks
- 7. Has a diagnosis of glaucoma, glaucoma suspect, ocular hypertension or prior glaucoma surgery

The following special populations will be excluded from this study:

- Adults unable to consent (including adults unable to read and understand English)
- Individuals who are not yet adults (infants, children, teenagers)
- Pregnant women
- Prisoners
- Employees of BostonSight

4.0 Vulnerable Populations

The following special populations will be excluded from this study:

- Adults unable to consent (including adults unable to read and understand English)
- Individuals who are not yet adults (infants, children, teenagers)
- Pregnant women
- Prisoners
- Employees of BostonSight

5.0 Number of Subjects

A minimum of 30 subjects will be enrolled in this study with 10 subjects in each of the three cohorts. This is a low risk study. We can expect an approximate 10% drop-out rate, so we will expect to recruit approximately 33 subjects; and the first 30 to be eligible and complete the study will be used for data analysis.

The first 10 subjects that are eligible to proceed and consented will be consecutively enrolled in the first cohort (scleral TonoPen). The second 10 subjects that are eligible to proceed and consented will be consecutively enrolled in the second cohort (scleral pneumatonometry). The third 10 subjects that are eligible to proceed and consented will be consecutively enrolled in the third cohort (Diaton). Sequential assignment allows for focus on one instrument and one technique at a time by one investigator.

6.0 Recruitment Methods

Recruitment will begin once IRB approval has been received and will occur through BostonSight. The subject pool will consist of patients who are actively coming through the clinic. We anticipate that all our subjects will be from the current patient population at BostonSight. Patients will be recruited via mailing and/or email and at office visits. If a patient is interested in participating in the study, they will be directed to the principal investigator or the study coordinator who will go over the study and ask the screening questions. If they are eligible based on the screening criteria, they will be invited for participation in the study. If the person calls to learn about the study, the investigator or coordinator will use the outline to determine initial eligibility. Current patients of BostonSight may also be recruited as a result of a search of the patient database. A partial HIPAA waiver is requested to permit the investigators to use the database to identify prospective patients.

7.0 Multi-Site Research Communication – N/A

8.0 Study Timelines

The total duration of the subjects' participation in the study will be approximately 1 visit. It is anticipated that to enroll all study subjects, it will take approximately 6 months.

The estimated date for completion of this study is 12 months after the start of recruitment.

The study visit will contain:

- a. Completion of informed consent
- b. Collection of baseline data of the eye
 - i. Corneal and conjunctival staining, Oxford grading
 - ii. Corneal IOP measurement via TonoPen
- c. Collection of baseline data on the PROSE device fit
- d. IOP measurement with lenses in place via one of three methods:
 - i. Scleral TonoPen
 - ii. Scleral pneumatonometry
 - iii. Diaton

The study visit will take approximately 65 minutes in total. All assessment performed will be for research purposes and not part of the subjects standard clinical care.

9.0 Study Endpoints

The study design allows for the subjects to serve as their own control. The subjects' baseline IOP will be measured with the standard clinical approach via corneal TonoPen. Corneal TonoPen was chosen as the control method for intraocular pressure measurements as it is a standard of care method and process used every day in clinical practice by ophthalmologists and optometrists. This will be compared to the IOP measurement obtained in the same subject with lenses in place.

The primary endpoints in this study are as follows:

- 1. Intraocular pressure
 - a. TonoPen, corneal without lens
 - i. Baseline, one measurement
 - b. TonoPen, scleral with lens
 - i. IOP and confidence level will be recorded
 - ii. Attempt 5 measurements maximum
 - Goal of achieving 3 measurements in total with confidence level of 90% of higher
 - iii. One measurement defined as a completed result or attempting to measure until the machine times out
 - c. Pneumatonometer, scleral with lens
 - i. Measurement in "manual IOP mode"
 - ii. IOP and standard deviation (SD) will be recorded for each measurement
 - iii. Attempt 10 measurements maximum
 - Goal of achieving 3 measurements in total with a SD of 2 mmHg or less
 - iv. One measurement defined as a completed result or attempting to measure until the machines times out
 - d. Diaton, transpalpebral with lens

- i. Up to 6 individual attempts are included in each complete measurement, with the instrument averaging the measurements for a result
- ii. Reliable average is confirmed:
 - When the instrument shows symbol <> and the mean IOP value is non-flickering
 - When the instrument shows symbol <> and the mean IOP value is flickering with a result of equal or less than 19 mmHg
- iii. Attempt 5 complete measurements maximum
 - Goal of achieving 3 reliable measurements
 - Reliability defined (per manufacturer Diaton, Ryazan State Instrument-Making Enterprise, www.diaton-tonometer.com) as:
 - a. +/- 2mmHg error in range 5-20mmHg
 - b. +/- 10% error in range 20-60mmHg

Correct calibration of each instrument will be ensured prior to the study per individual manufacturer's standards. The first measurement of every subject will not be included but will serve as one practice measurement to familiarize the subject with the measurement process.

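### The lens-off corneal TonoPen reference mixes method bias with true IOP change, so the stated comparison alone cannot show accuracy with the lens on

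*Protocol*

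**What the plan says.** - **Aim (Protocol 1.0).** The study is described as a "prospective study of the precision and accuracy of tonometry measurements with scleral lens wear". The intended use is also stated: "Data on precision and accuracy of these instruments in this pilot study aims to guide decision making in a full study" of how scleral lenses affect IOP.
- **Warning in the same section.** "Measuring IOP before insertion and after removal of the PROSE device likely does not correspond to the IOP when the lens is actively" worn.
- **Background (2.0).** Published work is said to suggest that IOP may go up in scleral lens wear, with varying methods and results. No size is given. The three test methods were chosen because "they are the only options currently available to measure IOP without corneal contact". A published equation for estimating corneal IOP from scleral pneumatonometry is mentioned as a possibility. It does not appear in the endpoints or the analysis.
- **Endpoints (9.0).** The reference is a single corneal TonoPen reading without the lens. Subjects act as their own control: "This will be compared to the IOP measurement obtained in the same subject with lenses in place".
- **Procedures (10.0).** The reference is step 6, after lens removal. The test readings are step 8, with the lens on, by one of three methods according to cohort. No test method is used with the lens off. Reapplication is not listed as a step, and no interval between steps 6 and 8 is fixed.
- **Cohorts (5.0).** Three groups of 10 are filled in turn, for example: "The second 10 subjects that are eligible to proceed and consented will be consecutively enrolled in the second cohort".
- **Analysis (23.0).** Baseline and test data are examined for differences with a broad list of tests and models.

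**The concern.** Accuracy of a lens-on reading is its closeness to the IOP that exists while the lens is on. The protocol's reference is the IOP at another moment, in another lens state, and Section 1.0 says that this likely differs from the quantity of interest. The comparison changes instrument or site and lens state in one move. A non-zero difference could therefore be method bias, a real change in IOP, or both. A zero difference could be two effects that cancel.

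This matters because the later study concerns the effect of the lens on IOP, which is the part that is mixed into the pilot's comparison. If IOP does rise in wear, a sound method would look as if it over-reads, and a method that reads low could look accurate. An instrument could then be carried into the full study, or dropped from it, for the wrong reason.

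**Working it through.** **Figures in the protocol.** None is given for the size of this difference. The only one used below is the visit length in Section 10.0, which reproduces: 20 + 10 + 2 + 4 + 5 + 20 + 4 = 65 minutes.

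**Notation.** Let b_on and b_off be the bias of the test method and site, relative to corneal TonoPen, with the lens on and off. Let N be the true IOP change between step 6 and step 8.

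**1. The stated comparison.** Mean(test, lens on − corneal TonoPen, lens off) = b_on + N. This is one equation per cohort with two unknowns. Pairing within subjects removes differences between people but leaves N in place.

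**2. Effect on the reading of a result.** The values of b_on and N below are assumed. The only error scale in Section 9.0 is the Diaton manufacturer's plus or minus "2mmHg error in range 5-20mmHg". It defines reliability for one device and serves here only as a yardstick.

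| Assumed N (mmHg) | Apparent difference, b_on = 0 | Apparent difference, b_on = −4 |
|---|---|---|
| −2 | −2 | −6 |
| 0 | 0 | −4 |
| +2 | +2 | −2 |
| +3 | +3 | −1 |
| +4 | +4 | 0 |
| +6 | +6 | +2 |

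An unbiased method falls outside ±2 mmHg once N exceeds 2 in either direction. A method that reads 4 mmHg low falls inside ±2 for every N from +2 to +6. At N = 0 nothing is distorted, but the planned data cannot show that N is 0.

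**3. Sample size does not help.** Assume bias 0, N = 3 mmHg and a standard deviation of differences of 3 mmHg. In 2,000 simulated trials, the 95% confidence interval for the mean difference, read as an interval for bias, contained the true bias in 19.65% of trials at n = 10 and in none at n = 100.

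**4. Comparing cohorts.** For cohorts i and j, the difference of the two comparisons is (b_i − b_j) + (N_i − N_j). It gives relative bias only if N is equal in different, consecutively enrolled groups, and it never gives b_i itself. Which method looks closest also depends on N. Suppose observed mean differences of +4 (scleral TonoPen), +1 (pneumatonometer) and −1 mmHg (Diaton), with a common N. The smallest absolute bias then belongs to Diaton at N = −1, to Diaton and pneumatonometer equally at N = 0, to the pneumatonometer at N = 1 or 2, and to scleral TonoPen at N = 3 or more.

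**5. The equation in Section 2.0.** It could at most supply an outside estimate of site bias for pneumatonometry. Subtracting that from b_on + N leaves N only if site bias is the same with the lens on and off. The other two cohorts have no such equation in the protocol.

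**6. Adding lens-off readings with the cohort's own tonometer.** Mean(test, off − corneal, off) = b_off, and mean(test, on − test, off) = N + (b_on − b_off). With the corneal mean, that makes three means for four unknowns (lens-off IOP, b_off, b_on, N). They separate only if b_on = b_off. That is uncertain in the scleral cohorts, because the lens "lands gently on the conjunctival tissue overlying the sclera", the kind of tissue that is probed.

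**7. Precision.** Repeat lens-on readings do not use the lens-off reference, so the mixing in step 1 does not reach them. They are spread over a block listed at 20 minutes, however, and Section 2.0 names settling of the lens as a possible source of pressure change. Their spread may therefore include true drift.

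**The case against.** The best defence is that no better reference exists. By the protocol's account nothing can be read from the cornea under the lens, so corneal TonoPen with the lens off is the practical choice for a small pilot. Sections 9.0 and 23.0 say only that the readings are compared and do not call the difference bias. An analysis plan that is not shown could define accuracy with care. The true change may also be zero.

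Much of this stands. The limit is partly inherent, and the size of any distortion is unknown. But the aim of lens-on accuracy, the readings and the comparison are all fixed in the protocol. No analysis can recover readings that were never taken, or separate the two parts without an outside assumption. An unavailable reference is a reason to narrow the claim.

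A reader might also infer more than the documents support:

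- **That the protocol plans to rank the instruments by accuracy.** It does not say so. It says only that the data will inform decisions for a full study.
- **That the direction of any IOP change is wholly open, or settled.** Section 2.0 suggests a rise and also reports variable results.
- **That separation is impossible in every cohort.** For pneumatonometry the equation offers a route, under the assumption in step 5.
- **That precision is untouched.** Possible drift during settling means this is not shown.

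**Conclusion.** The point holds. The stated comparison estimates method/site bias plus any true IOP change, and it cannot by itself support a conclusion on accuracy with the lens on. This follows from the design and does not depend on sample size or on the choice among the listed tests.

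The error equals N, mmHg for mmHg. The documents give no size for N, and it may be zero. The figures of 2 to 6 mmHg above are assumed values for illustration. If IOP rises, as Section 2.0 suggests it may, the distortion runs one way: methods appear to read higher than they do. Precision from repeat lens-on readings remains an aim that the design can address, subject to possible drift.

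**What to change.** **Needed, Protocol 1.0 and 9.0.** Define the lens-on versus lens-off difference as a combined method-and-lens difference, that is, agreement with lens-off corneal TonoPen. State that no conclusion on lens-on accuracy, and no choice of instrument for the full study on grounds of accuracy, is drawn from it alone. Keep precision from repeat lens-on readings, with a note that it may include true IOP drift while the lens settles.

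**Needed, Protocol 10.0.** Record the times of lens removal, reapplication and each reading. Times do not separate bias from IOP change, but they show the interval and allow drift to be examined.

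*Cost:* wording and time notes only, with no added measurement. The pilot claims less.

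**Optional and only partial.** Add lens-off readings with the cohort's own tonometer. Report lens-off agreement and same-instrument lens-on minus lens-off change separately, under the stated, untested assumption that method bias is the same with the lens on and off.

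*Cost:* an amendment and a longer visit. If time is proportional to attempts within the 20 minutes (assumption), three readings add 20 × 3/10 = 6 minutes for the pneumatonometer and 20 × 3/5 = 12 for TonoPen or Diaton, so 65 becomes 71 to 77 minutes (+9% to +18%). If a practice reading is also discarded, four readings add 8 to 16 minutes, giving 73 to 81. At the full attempt limits the visit is 85 minutes (+31%). The scleral cohorts would also have more conjunctival contact, with the risks named in Section 13.0, and contact shortly before reapplication might itself affect the lens-on readings.

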10.0 Procedures Involved

Once a subject has been identified, the initial visit will be scheduled.

During the visit:

- 1. Informed consent will be completed
- 2. Record the patient's general medical history and habitual contact lens information, including lens design, power, and diameter.
- 3. An investigator will conduct visual acuity assessments of both eyes (Snellen).
- 4. Assess the fit of the PROSE device via slit lamp assessment of both eyes.
- 5. Assess the cornea and conjunctiva of both eyes with the PROSE device on and off.
- 6. Measure corneal intraocular pressure of both eyes after PROSE device removal
- 7. The investigator will instill one drop of topical anesthetic in both eyes followed by a lubricating preservative-free artificial tear drop, such as Refresh Plus, prior to IOP measurements.
- 8. Measure intraocular pressure of both eyes with the PD on via (method depends on which cohort the subject is in):
 - a. Scleral TonoPen
 - b. Scleral pneumatonometry
 - c. Transpalpebral Diaton
- 9. Reassess the ocular surface of both eyes after intraocular pressure measurement at the slit lamp biomicroscope with and without fluorescein staining in order to rule out adverse events, such as conjunctival abrasion or erosion or other irritations.

Procedure	Length of Time	Frequency of Repetition
	Required for	

Informed consent & HIPAA	20 minutes	Once
General History and Medications	10 minutes	Once
Visual Acuity	2 minutes	Once
Slit-lamp Examination (with PD)	4 minutes	Once
Corneal IOP Measurement (TonoPen)	5 minutes	Once
IOP Measurement (One of the below will be completed)		
COHORT 1: Scleral TonoPen		5 (maximum)
COHORT 2: Scleral Pneumatonometer	20 minutes	10 (maximum)
COHORT 3: Transpalpebral Diaton		5 (maximum)
Slit-lamp Examination after measurement	4 minutes	Once
TOTAL TIME	65 minutes	

The testing descriptions are summarized in the table below:

Test	Description
General History	Participants will be asked questions about their general, ocular and
and Medications	medication use histories along with contact lens use history if applicable.
Lens Evaluation	The PROSE device fit and vision will be evaluated.
Visual Acuity	The participant's vision in each eye while wearing lenses will be measured with a high contrast visual acuity chart. The participant will be asked to cover one eye and read the chart, and this procedure will be repeated for the other eye.
Slit-lamp	The participant's front portion of each eye and contact lenses will be

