23.0 Data Management

Data will be stored in a study paper file at BostonSight. Electronic data will be stored on a password-protected computer in a locked office. All study data will remain at BostonSight for a minimum of 3 years following study completion. The principal investigator will be responsible for maintaining study data security and subject confidentiality, and the PI and the study coordinator will be responsible for receipt and transmission of the data. The investigative team and inspectors from regulatory agencies such as the US Food and Drug Administration will have access to the data if requested for study monitoring or an audit.

All collected data will be documented on study documents and analyzed for differences between baseline and test data. Hypothesis testing will be performed using statistical analyses including parametric or nonparametric comparisons (i.e., t-tests, signed-rank tests), analysis of variance, general linear models, correlation, or regression techniques.

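### A single corneal reading per eye as the reference leaves its repeatability unestimated and mixes its random error into the accuracy comparison

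*Protocol*

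**What the plan says.** Section 9 makes corneal TonoPen, without the lens, the control against which the same subject's lens-on pressure is compared. Item a.i sets it at "Baseline, one measurement". Section 10 has it taken in both eyes ("Measure corneal intraocular pressure of both eyes after PROSE device removal"), and the time-table row beginning "Corneal IOP Measurement (TonoPen" allows 5 minutes and a frequency of once. That is one reference reading per eye, with no stated acceptance rule.

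The lens-on methods in Section 9 are replicated, each under its own quality rule:
- Scleral TonoPen, up to 5 attempts: "Goal of achieving 3 measurements in total with confidence level of 90% of higher".
- Scleral pneumatonometer, up to 10 attempts: "Goal of achieving 3 measurements in total with a SD of 2 mmHg or less".
- Diaton, up to 5 complete measurements: "Goal of achieving 3 reliable measurements".

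Section 9 also discards the first measurement of every subject as practice, without naming the instrument. Section 1 gives the aim as the precision and accuracy of the lens-on measurements, to guide a full study. Section 23 says the data will be analysed for differences between baseline and test, then lists possible techniques ending in "correlation, or regression techniques".

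**The concern.** Accuracy can be judged here only through differences between the lens-on readings and the corneal reading. Each difference carries random error from both sides. The lens-on part can be estimated from its replicates; the corneal part cannot, because each eye has one reading. If the differences prove widely scattered, the pilot cannot say how much of the scatter belongs to the test tonometer and how much to the reference.

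This is fixed when the data are collected. No later analysis plan can recover a repeatability estimate from replicates that were never taken. At stake is how well the pilot informs the choice of instrument for the full study.

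**Working it through.** **1. Figures in the plan.** The plan gives counts but no pressure or error SDs: one reference reading per eye, a goal of three lens-on readings, and 10 subjects per cohort. There is no plan figure to reproduce on this point, so the SDs below are assumptions shown over a range.

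**2. Model.** For one eye, let the reference be the mean of m readings with single-reading error SD s_r. Let the test value be the mean of three readings with error SD s_x. Assume the two methods agree perfectly apart from random error.
- Variance of the difference = s_r²/m + s_x²/3.
- Reference share = (s_r²/m) / (s_r²/m + s_x²/3).
- Error part of the 95% limits of agreement = ±1.96 × SD of the difference.
- Expected mean difference = 0, whatever m is.

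**3. Results, with s_x = 2 mmHg.** For s_r = 2 and m = 1 the variance is 4 + 4/3 = 5.33, so SD 2.31, share 4/5.33 = 75% and limits ±4.5. For m = 3 it is 4/3 + 4/3 = 2.67, so SD 1.63, share 50% and limits ±3.2.

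| s_r (mmHg) | SD, one reading | Share | Limits | SD, three readings | Share | Limits | Narrowing |
|---|---|---|---|---|---|---|---|
| 1 | 1.53 | 43% | ±3.0 | 1.29 | 20% | ±2.5 | 15% |
| 2 | 2.31 | 75% | ±4.5 | 1.63 | 50% | ±3.2 | 29% |
| 3 | 3.21 | 87% | ±6.3 | 2.08 | 69% | ±4.1 | 35% |

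Narrowing is 1 minus the ratio of the two SDs. An error-free reference would give ±2.3.

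**4. What can be estimated.** The lens-on replicates give s_x. With m = 1 nothing gives s_r: the fellow eye has its own true pressure, and scleral repeatability with the lens on need not equal corneal repeatability. With m = 3 the within-eye SD of the corneal readings estimates s_r, and s_r²/3 can be subtracted from the variance of the differences.

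**5. Correlation and slope.** Let the true between-eye SD be s_t.
- Correlation = √[ s_t²/(s_t² + s_r²/m) × s_t²/(s_t² + s_x²/3) ].
- With s_t = 3 and s_r = s_x = 2: one reading gives √(9/13 × 9/10.33) = 0.78; three give 0.87.
- Over s_t 2 to 4 and s_r 1 to 3, with s_x = 2: 0.48 to 0.93 with one reading, 0.65 to 0.95 with three.
- Slope of test on corneal = s_t²/(s_t² + s_r²/m): 0.69 with one reading, 0.87 with three.
- Slope of corneal on test = s_t²/(s_t² + s_x²/3) = 0.87, whatever m is.

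A simulation of the central case gave the same values, with mean difference 0.00. The exclusion "Has a diagnosis of glaucoma, glaucoma suspect, ocular hypertension or prior glaucoma surgery" can be expected to reduce s_t, which strengthens attenuation, but the protocol gives no figure for by how much.

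**6. Time.** The Section 10 table sums to 20 + 10 + 2 + 4 + 5 + 20 + 4 = 65 minutes, with no slack. It allots 20 minutes to lens-on readings. If the maxima of 5 or 10 are per eye, that is 10 or 20 attempts at 2 or 1 minutes each. At that rate six corneal readings would take 6 to 12 minutes, against the 5 allotted.

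**The case against.** The strongest reply is that this is an efficiency matter in a 30-subject pilot, neither an error nor a contradiction, and that its consequences are limited. Much of that stands. Random reference error does not bias the mean paired difference; it only widens its interval. The within-device precision of the lens-on readings, half of the stated aim, is untouched. All cohorts use the same reference method, so its error adds noise without systematically favouring one tonometer.

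A reader might infer that the regression in Section 23 is biased, or that correlation is to serve as the measure of accuracy. The document supports neither. Section 23 is an open list; it fixes no predictor and never calls correlation an accuracy measure. Reference error flattens the slope only if corneal pressure is the predictor. The only predictive use mentioned, in Section 2, runs the other way, from scleral reading to corneal pressure. The choice among these techniques properly belongs to an analysis plan.

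A reader might also take 75% and 29% as general results. They hold only when the two reading SDs are equal.

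Section 9 justifies the control as the standard clinical approach. That supports the instrument rather than the single reading. What the reply does not answer is that the reference's repeatability will be unknown and cannot be recovered afterwards.

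**Conclusion.** The point holds as an inexpensive improvement to data collection. One corneal reading per eye leaves the reference's error unestimated and mixed into the differences used to judge accuracy. Limits of agreement are widened and any correlation is attenuated; the average difference and lens-on repeatability are not biased.

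The size depends on assumed SDs. With a test SD of 2 mmHg and a reference SD of 1 to 3 mmHg, moving from one to three reference readings cuts the reference's share of the random variance from about 43–87% to 20–69%, and narrows the error part of the limits by about 15–35%.

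The calculation omits eye-specific disagreement between methods and any true effect of the lens on pressure. It would be too strong to infer that replication makes the comparison clean: some reference error remains. Section 1 itself doubts that lens-off pressure corresponds to lens-on pressure, and more corneal readings do not resolve that.

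**What to change.** In Section 9 item a.i, and in the frequency column of the Section 10 time table, specify three corneal TonoPen readings per eye. Use their mean as the reference and report their within-eye SD, so that reference error can be separated from test-device error.

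State in Section 9 whether the discarded practice measurement applies to the corneal reading. In the Section 10 order the corneal reading comes first. Read literally, the rule could therefore remove the only reference reading for one eye of each subject, so the two statements need reconciling.

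The cost is two more brief corneal contacts per eye, under the anesthetic that Section 10's test descriptions already specify for this measurement, and possibly a few more minutes. The 5-minute slot and the 65-minute total should be rechecked. No change to Section 23 is needed for this point.
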